## **6.3.2** Permitted Medications

The investigator may prescribe any concomitant medication or therapy deemed necessary to provide adequate supportive treatment throughout the study, including those listed below:

Standard supportive treatment (antiemetics, antidiarrheals, anticholinergics, spasmodic drugs, antipyretics, antihistamines, analgesics, and other medications designed to treat the symptoms or signs) will be administered as clinically indicated according to local standard of care and when deemed necessary by the investigator.

- Growth factor support, erythropoietin, and blood product transfusion are allowed for the treatment of symptoms or signs of neutropenia, anemia, or thrombocytopenia according to local standard of care.
- Infectious complications with documented evidence should be treated with oral or intravenous antibiotics, or other anti-infective drugs that the investigator considers appropriate for the infectious condition according to local standards

of care. If clinically indicated, the investigator may administer prophylactic anti-infective therapy to patients according to local standards of care.

- Prevention of tumor lysis syndrome (TLS): For patients with elevated risk of TLS such as high tumor load and renal impairment, adequate hydration and alkalinization should be performed during treatment according to clinical practice, and blood chemistry should be closely monitored.
- Prevention and treatment of HBV activation.
- Other medications for concomitant diseases: Treatment for hypertension, diabetes, etc.
- If a patient experiences an AE during study treatment, the investigator should provide appropriate treatment according to clinical practice, including but not limited to antiemetics, hepatoprotective drugs, drugs for increasing leukocyte, transfusion/blood products, anti-infection drugs, and drugs causing QTc prolongation.

### **6.3.3** Prohibited Medications

The following medications are prohibited during the study. The clinical research associate (CRA) must be notified in advance (or as soon as possible thereafter) of any circumstances requiring prohibited or restricted therapy. In case of any queries or concerns about the use of any of the following prohibited or restricted medications, the investigator must consult the CRA for guidance.

- Any anti-cancer chemotherapy, immunotherapy, targeted therapy, experimental therapy, or hormone therapy (except for therapy with luteinizing hormone-releasing hormone). However, supportive therapeutic drugs, including bisphosphonates and hormone replacement drugs, are allowed.
- Hormonal contraceptives: Hormonal contraceptives can enhance the thrombotic effect of thalidomide.
- Azelastine (nasal): Thalidomide tablets can enhance azelastine's depressant effect on the central nervous system.
- Ethanol: Concomitant administration with methotrexate tablets will increase the risk of drug reactions and liver toxicity, and long-term use may cause liver damage.
- Kanamycin: Concomitant administration with methotrexate tablets will affect its therapeutic effect and may increase the risk of other reactions, such as nausea, vomiting, diarrhea, and other gastrointestinal symptoms.
- Triamterene: Concomitant administration with methotrexate tablets will lead to increased serum concentration, increase toxicity and side effects, and also cause renal excretion disorders, resulting in kidney injury. Methotrexate tablets need to be administered under the guidance of the investigator.

- Carbonic anhydrase inhibitor: Long-term use of carbonic anhydrase inhibitor in combination with prednisone may lead to hypocalcemia, osteoporosis, etc. which should be avoided.
- COVID-19 vaccines (adenovirus vector, messenger RNA), vaccines (inactivated): The immune efficacy of these vaccines may be reduced.

# 6.4 Source and Use of Study Drugs

The study drugs in this study include thalidomide, methotrexate, and prednisone.

### Thalidomide:

Commercially available thalidomide tablets will be used in this study. Each site will use commercially available thalidomide tablets for treatment according to clinical needs. Refer to local prescribing information for dosage form, packaging, and storage of thalidomide.

#### **Methotrexate:**

Commercially available methotrexate tablets will be used in this study. Each site will use commercially available methotrexate tablets according to clinical needs. Refer to local prescribing information for dosage form, packaging, and storage of methotrexate.

#### **Prednisone:**

Commercially available prednisone tablets will be used in this study. Each site will use commercially available prednisone according to clinical needs. Refer to local prescribing information for dosage form, packaging, and storage of prednisone.

# 7 Adverse Reactions and Dose Adjustment

## 7.1 Common Adverse Reactions of Thalidomide

# **Teratogenic Effects:**

Thalidomide should not be used in pregnant women. When administered to pregnant women, thalidomide may cause fetal harm. Thalidomide is a highly potent human teratogen that induces severe and life-threatening birth defects at high frequencies, even with single dose. Approximately 40% of infants whose mothers have received this drug are reported to have died at birth or shortly after birth. Pregnant patients will not be enrolled in the study.

## **Constipation:**

Administration of thalidomide may irritate the gastrointestinal tract, thus resulting in constipation.

#### Nausea:

Nausea ranks as the second most common adverse reaction in the digestive system, most nausea is mild to moderate in severity.

#### **Venous and Arterial Thromboembolism:**

Thalidomide may increase the risk of venous thromboembolism (eg, deep vein thrombosis and pulmonary embolism), which may be significantly increased when thalidomide is used in combination with standard chemotherapeutic agents including dexamethasone.

## **Peripheral Neuropathy:**

Thalidomide may cause permanent nerve damage. Peripheral neuropathy is common (≥10%) and potentially irreversible with the serious adverse reaction to the treatment with thalidomide. Peripheral neuropathy usually develops after prolonged use over several months. However, peripheral neuropathy after relatively short-term use has also been reported. The correlation with cumulative dose is unknown. Symptoms may appear for some time after the discontinuation of treatment with thalidomide, and these symptoms may disappear slowly or completely.

### Neutropenia:

White blood cell (WBC) count decreased with the clinical use of thalidomide, including neutropenia, have been reported.

### **Thrombocytopenia:**

Grade 3 or 4 thrombocytopenia with the clinical use of thalidomide has been reported.

## **Severe Skin Reactions**

Severe skin reactions have been reported for the treatment with thalidomide, including Stevens-Johnson syndrome (SJS), toxic epidermal necrolysis (TEN), and drug reaction

with eosinophilia and systemic symptoms (DRESS). DRESS may result in skin reactions (eg, rash or exfoliative dermatitis), eosinophilia, fever, and/or lymphadenopathy with systemic complications, such as hepatitis, nephritis, pneumonia, myocarditis, and/or pericarditis.

## **Allergy**

Hypersensitivity reactions, including angioedema and allergic reactions to thalidomide, have been reported. Signs and symptoms include macular rash, which may be associated with fever, tachycardia, and hypotension.

#### Seizure

Although no premarketing controlled clinical trials have been reported, seizures, including severe convulsions, have been reported during the approval of thalidomide in clinical practice.

### **Tumor Lysis Syndrome**

Monitor patients at risk for TLS (eg, patients with high tumor load before treatment)

#### **HIV Viral Load Increased**

In a randomized, placebo-controlled trial of thalidomide in HIV seropositive patients, increased plasma HIV RNA levels were observed with the median change from placebo of  $0.42 \log 10$  copies of HIV RNA/mL (p = 0.04). A similar trend was observed in another unpublished study of HIV seropositive patients. The clinical significance of this increase is unknown. Both studies were conducted before the implementation of highly active antiretroviral therapy.

## Bradycardia

Bradycardia has been reported to be associated with the use of thalidomide. There are reported cases of bradycardia, some requiring medical intervention. The clinical significance and underlying etiology of bradycardia found in some patients treated with thalidomide are unknown.

## **Somnolence**

Thalidomide often causes somnolence. Patients should be advised to avoid somnolence and not to take other medications that may cause somnolence without medical advice.

## 7.2 Common Adverse Reactions of Methotrexate

Methotrexate, an organic compound, is mainly used as an antifolate antineoplastic drug, which can inhibit dihydrofolate reductase, thereby impeding synthesis in tumor cells and inhibiting the growth and proliferation. Refer to the locally approved labeling (eg, refer to local prescribing information) for details of methotrexate. In this study, low-dose methotrexate is administered orally at 10 mg/m², once a week. The most common adverse reactions of low-dose methotrexate are summarized below.

# **Elevated Transaminase**

Elevated transaminase is the most common adverse reaction of methotrexate and also the most common non-hematological AE, which is usually mild in severity. Liver function tests should be performed regularly after administration. Although these mild AEs will not lead to the discontinuation of methotrexate, this drug should be used with caution.

## Cytopenia

In patients receiving low-dose methotrexate, cytopenia (neutropenia, thrombocytopenia, and anemia) is generally reported as Grade 1 or 2, but treatment-emergent Grade 3 or 4 cytopenia (neutropenia, thrombocytopenia, and anemia) is also reported. Anemia is the most common hematological adverse reaction, followed by neutropenia and thrombocytopenia.

### Nausea and vomiting

Nausea and vomiting are another common non-hematological AEs. Other frequently reported gastrointestinal events included diarrhea, abdominal pain, cholecystitis, and gallstones. These events are rarely serious. If symptoms are severe or persist for a long time, follow the guidelines for dose adjustment in the protocol.

#### **Stomatitis**

Stomatitis has an incidence of < 10% and is generally of Grade 1 or 2. Symptoms may improve after symptomatic treatment.

#### Rash

Rash can be manifested as erythematous rash, alopecia, pruritus, redness and swelling, with an incidence of <3%. There are rare case reports of severe skin reactions, including toxic epidermal necrolysis, Stevens-Johnson syndrome, exfoliative dermatitis, cutaneous necrosis, and erythema multiforme.

#### 7.3 Common Adverse Reactions of Prednisone

Prednisone is a glucocorticoid with anti-inflammatory, anti-allergic, antirheumatic and immunosuppressive effects. It is a commonly used medication for hematologic disorders. Due to its frequent clinical use, details will not be provided in this protocol.

## Water-electrolyte Disturbance

Water-electrolyte disturbance includes sodium retention, fluid retention, congestive heart failure in susceptible patients, potassium loss, hypokalemic alkalosis, and hypertension.

### Musculoskeletal System

Musculoskeletal system events include myasthenia, steroid myopathy, muscle tissue loss, osteoporosis, tendon rupture (especially Achilles's tendon rupture), vertebral compression fracture, aseptic necrosis of femoral and humeral heads, and pathological fracture of diseased long bone.

#### **Digestive System**

Digestive system events include ulcer (possible perforation and bleeding), pancreatitis, abdominal distension, and ulcerative esophagitis.

### Skin/Subcutaneous Tissue

Difficult-to-heal wounds, thin fragile skin, petechiae and ecchymosis, facial erythema, and increased sweating may suppress reactions to skin tests.

### **Metabolic System**

Metabolic system event includes negative nitrogen balance caused by protein catabolism.

## **Nervous System**

Elevated intracranial pressure, vertigo and headache with papilledema (pseudoencephaloma) usually occur after treatment.

## **Endocrine System**

Endocrine system events include irregular menstruation, development of Cushingoid syndrome, secondary adrenocortical and pituitary unresponsiveness (especially in stressful states such as trauma, surgery or disease), inhibition of growth and development in children, reduced carbohydrate tolerance, manifestations of latent diabetes, increased demand for insulin or oral hypoglycemic agents in diabetic patients.

## Eyes

Eyes events include posterior subcapsular cataract, elevated intraocular pressure, glaucoma, and proptosis (exophthalmos).

### **Anaphylaxis**

Anaphylaxis events include urticaria and other allergy, anaphylaxis or hypersensitivity.

# 7.4 Guidelines for Dose Adjustment and Discontinuation

In the event of toxicity, the investigator should accurately assess the severity of AEs and serious adverse events (SAEs) based on the patient's condition and the National Cancer Institute (NCI) Common Terminology Criteria for Adverse Events (CTCAE, Version 5.0). Appropriate medication (including infusions, cytokine growth factors, antiemetics, antidiarrheals, etc.) should be administered to treatment AEs. All AEs will be assessed from the time of the first dose of the study treatment until the final study visit. Patients who have experienced AEs may be followed up after the EOS visit for additional assessments until the AE resolves or is deemed stable.

For patients who are unable to tolerate the protocol-specified administration regimen, treatment discontinuation or dose adjustments are allowed. Before treatment discontinuation and dose adjustment, the attribution of AEs to the 3 drugs (thalidomide, methotrexate, and prednisone) should be determined. For non-hematological toxicities attributable to methotrexate and prednisone (not thalidomide), administration of thalidomide may be continued.

# 7.4.1 Dose Adjustment and Discontinuation of Thalidomide

If thalidomide-related peripheral neuropathy occurs, neuroprotective drugs can be used as appropriate; if there are  $\geq$  Grade 2 or Grade 1 side effects with pain, reduce the dose by 1 dose level and discontinue in those without improvement. See Appendix 4 for details of thalidomide neurotoxicity grading and dose adjustment.

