# 6 Treatments

# **6.1 Treatment Regimen**

Treatment will be provided in 3-month cycles. Patients will receive thalidomide of 50 to 100 mg orally QD before bedtime, methotrexate of 10 mg/m² orally once weekly, and prednisone of 0.5 to 1 mg/kg orally QOD. Prednisone will be tapered after 3 months of dosing and dosed for up to 6 months. Methotrexate will be dosed for up to 1 year. Thalidomide will be dosed for up to 2 years or discontinued at the investigator's discretion based on clinical symptoms. Efficacy was evaluated after 3 months of treatment, if PR or above response to treatment, the initial treatment regimen will be continued. If there is no clinical benefit after 6 months of initial treatment, patients will switch to the second-line treatment was and will be withdrawn from the study.

Dosage and administration for study drugs are shown in the following table:

TPM Regimen	Dosage and Administration
Methotrexate	10 mg/m  orally, once weekly
Prednisone	0.5–1 mg/kg orally, every other day
Thalidomide	50–100 mg orally, once daily before bedtime

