# **6.2 Administration of Study Drugs**

## Thalidomide:

Thalidomide administration will be started at 50 mg QD to observe whether there are adverse reactions such as rash and numbness of extremities, and then increased to 100 mg QD, if tolerated, for 1 week. Attention will be paid to observe adverse reactions such as peripheral neuritis. Thalidomide administration will be maintained for a total of 2 years and whether to discontinue will be determined based on the clinical symptoms. If the patient has a study drug-related adverse reaction, the dosage will be adjusted according to the dose adjustment guidelines in Section 7.4.1.

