# **10.2** Safety Evaluation

If a patient completes at least 1 month of effective treatment, the patient will be analyzed for safety. The tolerability of treatment will be assessed by evaluating laboratory parameters and AEs. The incidence of all AEs during the treatment and up to 30 days after the last drug administration will be recorded.

AEs will be classified by severity, duration, and frequency. Details of AEs will be listed by patients, including time of onset, duration, toxicity grade, corrective treatment, outcome, and relationship to the investigational product. Safety parameters will be assessed by 2 independent investigators who will assess severity and treatment each time.

Study drug should be discontinued for any uncontrolled non-hematological toxicity that may be associated with the study drug and of Grade 3 or higher, and for any hematological toxicity that meets the criteria. For patients requiring full-dose anticoagulation (eg, heparin), the study drug should be interrupted until the anticoagulation is stable. For patients requiring an invasive procedure or surgery, the study drug must be interrupted. Any other clinically important events, in which the investigator may deem appropriate dose delays, must be discussed with the CRA. Details of drug adjustment and discontinuation criteria, refer to Section 7.4.

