Appendix 4. Thalidomide Neurotoxicity Grading and Dose Adjustment

	0	1	2	3	4
	Normal	Asymptomatic: Loss of deep tendon reflexes or paresthesia (including tingling), but not interfering with function	Sensory alteration or paresthesia (including tingling) interfering with function but not with activities of daily living	Sensory alteration or paresthesia interfering with activities of daily living	Disabling
Not applicable	No action	Thalidomide reduced by one dose level	Thalidomide reduced by two dose levels	Thalidomide withheld	Thalidomide withheld
Slight pain but not interfering with function	No action	Thalidomide reduced by two dose levels	Thalidomide discontinued	Thalidomide withheld	Thalidomide withheld
Moderate pain (interfering with function but not with activities of daily living)	Thalidomide reduced by one dose level	Thalidomide reduced by two dose levels	Thalidomide withheld	Thalidomide withheld	Thalidomide withheld
Severe pain (interfering with activities of daily living)	Thalidomide reduced by one dose level	Thalidomide reduced by two dose levels	Thalidomide withheld	Thalidomide withheld	Thalidomide withheld
Disabling	Thalidomide withheld	Thalidomide withheld	Thalidomide withheld	Thalidomide withheld	Thalidomide withheld

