## Notes:

Withheld: Thalidomide should be withheld for 2 weeks until the toxicity returns to Grade 1 or better condition.

Reduced by one dose level: Thalidomide reduced from 100 mg/d to 50 mg/d.

Reduced by two dose levels: Thalidomide reduced from 100 mg/d to 50 mg, every other day.

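### For thalidomide neuropathy, Section 7.4.1 orders a one-level dose reduction, but the Appendix 4 grid it points to orders a stricter first step in every matching cell

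*Supplement*

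**What the plan says.** All references are to protocol version 2.0.

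- **Section 7.4.1** sets the trigger at neuropathy of Grade 2 or higher, or Grade 1 with pain. The action is to "reduce the dose by 1 dose level and discontinue in those without improvement". The next sentence is a pointer: "See Appendix 4 for details of thalidomide neurotoxicity grading and dose adjustment".
- **Appendix 4** is a grid of five pain rows by five neuropathy grades (0 to 4), with an action in each cell. For several of the states named in Section 7.4.1 the entry is "Thalidomide reduced by two dose levels"; for most of the others it is withholding.
- **The notes to Appendix 4** define the actions. One level is 100 mg/d to 50 mg/d. For two levels: "Reduced by two dose levels: Thalidomide reduced from 100 mg/d to 50 mg, every other day". For withholding: "Thalidomide should be withheld for 2 weeks until the toxicity returns to Grade 1 or better condition". They do not define discontinuation and give no restart dose after withholding.
- **Section 6.2** says that, for a drug-related reaction, "the dosage will be adjusted according to the dose adjustment guidelines in Section 7.4.1".
- **Section 6.1** makes 50 mg a permitted daily dose: "Patients will receive thalidomide of 50 to 100 mg orally QD before bedtime". Section 6.2 starts every patient at 50 mg.
- **Section 7.4**, the parent of 7.4.1, says in general terms that toxicity severity is assessed with CTCAE Version 5.0.

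**The concern.** A short rule followed by a pointer to a table should agree with the table. Here the sentence in Section 7.4.1 and the grid prescribe different first doses for the same event, and nothing says which one prevails. An investigator who applies Section 7.4.1 as written keeps the patient on 50 mg every day in states where the grid halves that again or stops the drug.

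The stake is patient safety and uniform conduct. Section 7.1 describes thalidomide neuropathy as common (10% or more) and possibly permanent, and thalidomide can run for up to two years. Section 2.6.2 lists peripheral neuropathy among the main expected reactions, mostly Grade 1 or 2. It reports no Grade 3 or higher reaction in the preliminary data apart from one nausea. The Grade 1-2 cells are therefore the ones most likely to be used. In a multicentre trial, sites could respond differently to the same event and each could cite the protocol in support.

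**Working it through.** There is no planned figure to reproduce. The check sets the two rules side by side, cell by cell.

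**Grid in Appendix 4** (R1 = one level down, R2 = two levels down, W = withheld, D = discontinued):

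| Pain | Gr 0 | Gr 1 | Gr 2 | Gr 3 | Gr 4 |
|---|---|---|---|---|---|
| None | no action | R1 | R2 | W | W |
| Slight | no action | R2 | D | W | W |
| Moderate | R1 | R2 | W | W | W |
| Severe | R1 | R2 | W | W | W |
| Disabling | W | W | W | W | W |

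**Cells that meet the Section 7.4.1 trigger**

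- Grade 1 with pain: 4 cells. Grade 2, any pain row: 5 cells. Grades 3-4: 2 × 5 = 10 cells.
- Total: 4 + 5 + 10 = 19 of 25. Outside the trigger: 25 − 19 = 6.

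**What the grid orders in those cells**

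- Grade 1 with pain: R2 in 3 (slight, moderate, severe), W in 1 (disabling).
- Grade 2: R2 in 1 (no pain), D in 1 (slight), W in 3 (moderate, severe, disabling).
- Grades 1-2 together: R2 in 3 + 1 = 4, D in 1, W in 1 + 3 = 4; 4 + 1 + 4 = 9. All 9 are stricter than one level down.
- Grades 3-4: W in 10 of 10.
- One-level steps inside the trigger: 0 of 19. The grid uses R1 in only 3 cells (Grade 1 without pain; Grade 0 with moderate or severe pain), and all 3 are among the 6 outside the trigger.

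**Alternative reading of the trigger.** If pain is required at both grades, the Grade 2 no-pain cell drops out: 9 − 1 = 8, and all 8 remain stricter.

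**Dose in the first 14 days, starting from 100 mg/d**

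- One level (Section 7.4.1): 50 mg × 14 = 700 mg.
- Two levels (grid): 50 mg × 7 = 350 mg.
- Withheld or discontinued (grid): 0 mg.

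**After the first two weeks.** Suppose a withheld patient recovers by day 14. Total dose to day 28 then depends on a restart dose that the protocol does not give:

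- Restart at 100 mg/d (assumed): 100 mg × 14 = 1,400 mg.
- Restart at 50 mg/d (assumed): 50 mg × 14 = 700 mg.
- One level throughout (Section 7.4.1): 50 mg × 28 = 1,400 mg.

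**Two further faults in the grid**

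- At Grade 2, slight pain leads to discontinuation, while moderate, severe and disabling pain lead only to a temporary hold. The action becomes milder as pain worsens.
- Both reduction steps are written only from 100 mg/d, so a patient taking 50 mg/d has no defined step.

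**The case against.** **The pointer may settle precedence.** Section 6.2 leads to 7.4.1, and 7.4.1 leads to Appendix 4 for dose adjustment as well as grading. A summary followed by a detailed table is usually read with the table as operative. Section 6.1 also lets the investigator stop thalidomide on clinical grounds, so nothing forbids a stricter step. A careful investigator may well use the grid. That does not mend the text: details should expand a rule, and this table contradicts the sentence before it in every matching cell.

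**The grades may not be the same.** Section 7.4 cites CTCAE 5.0 generally. If Section 7.4.1 means CTCAE grades, the cell counts are not a like-for-like match. The pointer to Appendix 4 for neurotoxicity grading favours the appendix scale but does not prove it. The other reading leaves two scales applied to one event without saying so, which also needs correcting.

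**The single discontinued cell may be a slip.** The notes do not define that action. If it means withheld, the split becomes 4 two-level and 5 withheld. It is still 9 of 9 stricter, and the pain-ordering fault disappears.

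**Section 10.2 as a third conflicting rule.** A reader might infer this from "Study drug should be discontinued for any uncontrolled non-hematological toxicity that may be associated with the study drug and of Grade 3 or higher". The documents do not support it. The sentence is limited to uncontrolled toxicity, which is compatible with stopping patients who do not improve, and the same paragraph refers to Section 7.4 for adjustment and discontinuation criteria.

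**The grid as stricter throughout.** A reader might also infer that the grid always gives less drug. Only the first step shows that. As the 28-day figures show, a hold followed by a restart at 100 mg/d would equal the one-level rule by day 28 and exceed it afterwards.

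**Conclusion.** The inconsistency is real and should be fixed. Section 7.4.1 orders a first step that the grid does not order in any of the 19 cells meeting its trigger. In the 9 Grade 1-2 cells (8 on the narrower reading of pain) the grid is stricter each time, and in the 10 Grade 3-4 cells it withholds. From 100 mg/d the gap over the first two weeks is 700 mg against 350 mg or 0 mg.

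The counts assume that Section 7.4.1 uses the Appendix 4 grades. The direction of the difference is established for the first step only. The number of patients affected cannot be estimated from the documents. The primary endpoint analysis is unaffected, so this is a matter of patient safety and consistent conduct.

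**What to change.** In Section 7.4.1, replace the one-level sentence with a statement that the Appendix 4 grades and grid govern the first dose step for neuropathy. Keep discontinuation in patients who do not improve as the follow-on rule after any reduction or hold, because the grid contains no such rule.

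In Appendix 4:

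- correct the Grade 2 slight-pain cell so that actions do not become milder as pain worsens;
- define the one-level and two-level steps for a patient on 50 mg/d;
- state the restart dose after withholding.

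Section 10.2 needs no change on this account.

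The cost is amendment wording, with no added visits, tests or patients. The downside is slightly lower thalidomide exposure in affected patients, by an amount that depends on the restart dose chosen.

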#### 5.3 Withdrawal Criteria

- 1. Patients withdraw the ICFs
- 2. Patients experience PD or death
- 3. Patients experience intolerable toxicity that cannot be relieved after symptomatic treatment
- 4. Patients are unwilling to continue treatment
- 5. There was no clinical benefit for more than half a year
- 6. Delayed dosing for more than 4 weeks and patients are judged by investigators to be unsuitable for further dosing

- 7. Pregnancy
- 8. Lost to follow-up
- 9. Treatment should be discontinued based on the best interests of the patients at the investigator' discretion
- 10. Patients does not comply with the protocol, and the investigator deems it necessary to discontinue the treatment
- 11. The collaborator or regulatory authority notifies to end the clinical study.

If treatment discontinuation is due to any of the above reasons, the investigator must notify the Principal Investigator and complete the case summary page in the case report form (CRF), along with the date and reason for the treatment discontinuation. If treatment discontinuation is due to an AE, the AE will be followed up until it is resolved and stable.

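### For thalidomide neuropathy of Grade 2 or higher, or Grade 1 with pain, Section 7.4.1 orders a one-level reduction that Appendix 4 orders in none of the 19 matching cells, and no text says which governs

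*Supplement*

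**What the plan says.** All references are to protocol version 2.0.

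- **Section 7.4.1.** For thalidomide-related neuropathy of Grade 2 or higher, or Grade 1 with pain, the instruction is "reduce the dose by 1 dose level and discontinue in those without improvement". The next sentence sends the reader to Appendix 4 for grading and dose adjustment.
- **Appendix 4, table.** It crosses sensory grade (0 to 4) with pain (none, slight, moderate, severe, disabling). Within the Section 7.4.1 trigger it uses three actions: "Thalidomide reduced by two dose levels", "Thalidomide discontinued" and a hold.
- **Appendix 4, notes.** The actions are distinct: "Reduced by one dose level: Thalidomide reduced from 100 mg/d to 50 mg/d"; two levels means 100 mg/d to 50 mg every other day; and "Withheld: Thalidomide should be withheld for 2 weeks until the toxicity returns to Grade 1 or better condition".
- **Section 6.2.** Thalidomide starts at 50 mg daily and rises to 100 mg if tolerated. Dose changes for adverse reactions follow Section 7.4.1.
- **Section 10.2.** "Study drug should be discontinued for any uncontrolled non-hematological toxicity that may be associated with the study drug and of Grade 3 or higher". The same paragraph ends: "Details of drug adjustment and discontinuation criteria, refer to Section 7.4".
- **Section 5.3, criterion 3.** A withdrawal reason is "Patients experience intolerable toxicity that cannot be relieved after symptomatic treatment".

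**The concern.** A sentence and the table it cites should give the same action for the same patient, and here they do not. Section 7.1 describes peripheral neuropathy under thalidomide as common (10% or more) and potentially irreversible, and treatment may last two years at several centres. Two investigators could both follow the protocol and take different first steps in identical patients. The sentence is the milder of the two at that step, so a site that reads only Section 7.4.1 keeps the patient on more drug than the table allows.

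**Working it through.** The plan gives no figure to reproduce. The check sets each Appendix 4 cell that meets the Section 7.4.1 trigger against a one-level reduction, with Grade read on the Appendix 4 scale.

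**1. Cells at Grade 1 with pain and at Grade 2**

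| Pain | Grade 1 | Grade 2 |
|---|---|---|
| None | outside the trigger | two levels down |
| Slight | two levels down | discontinued |
| Moderate | two levels down | withheld |
| Severe | two levels down | withheld |
| Disabling | withheld | withheld |

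Grade 1 with pain gives 4 cells and Grade 2 gives 5, so 4 + 5 = 9: two levels down 4, withheld 4, discontinued 1.

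**2. Grades 3 and 4.** 2 × 5 = 10 cells, all withheld.

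**3. Total.** 9 + 10 = 19 cells: two levels down 4, discontinued 1, withheld 4 + 10 = 14. One level down: 0 of 19. The table orders a one-level reduction only outside the trigger, at painless Grade 1 and at Grade 0 with moderate or severe pain.

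**4. Alternative reading of the trigger.** If the pain condition qualifies both grades, the painless cells at Grades 2, 3 and 4 drop out: 19 − 3 = 16 cells, of which 9 − 1 = 8 lie at Grades 1 and 2. Matches remain 0.

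**5. First step from 100 mg/d in the 9 cells, with the dose over 14 days**

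- Section 7.4.1: 50 mg/d, 14 × 50 = 700 mg.
- Appendix 4, two levels down (4 cells): 50 mg every other day, 7 × 50 = 350 mg.
- Appendix 4, withheld (4 cells) or discontinued (1 cell): 0 mg.

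Beyond day 14 the held cells cannot be compared, because no restart dose is given.

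**6. Does another rule decide?** Section 6.2 points to 7.4.1, 7.4.1 points to Appendix 4, and 10.2 points back to 7.4. None ranks the sentence against the table. Section 10.2's own rule starts at Grade 3 and requires uncontrolled toxicity. Of the 9 cells, 4 carry severe or disabling pain (Grades 1 and 2 for each). The general grades in Section 10.1 put inability to perform daily activities at Grade 3 and a disabling event at Grade 4. If the pain is graded that way and is uncontrolled, Section 10.2 could apply. It would order discontinuation, which is the first action of neither text in those 4 cells, and it then refers back to Section 7.4. The cells clearly outside Section 10.2 number 9 − 4 = 5, or 8 − 4 = 4 on the reading in step 4.

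**7. If the neuropathy does not improve.** Section 7.4.1 stops the drug. In the three held Grade 2 cells the patient also stays off drug, because the hold lasts until Grade 1 or better. The table becomes the milder text only in the 4 two-level cells, where it gives no follow-on step, and at Grade 1 with disabling pain, where the grade for ending the hold is already met.

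**8. Can the table simply be declared binding?** Not as it stands. Grade 2 with slight pain is discontinued, while Grade 2 with worse pain is only withheld. No restart dose follows a hold. Levels are written only from 100 mg/d: one level below 50 mg/d can be inferred as 50 mg every other day, but a two-level reduction from 50 mg/d (the 4 two-level cells) has no value.

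**The case against.** The best defence is that precedence is implied. The chain of cross-references ends at Appendix 4, and a summary sentence that defers to a detailed table is ordinarily read as yielding to it. On that reading, the discontinuation clause in Section 7.4.1 is the follow-on step to the table. This is a reasonable inference and it shapes the fix. It is still not a stated rule: Section 6.2 names 7.4.1 as the dosing guideline, and details would normally elaborate a rule, whereas these differ from it in every triggered cell.

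The second defence is discretion. Section 5.3 allows withdrawal in the patient's best interests (criterion 9), and after a dosing delay of more than 4 weeks if the patient is judged unsuitable (criterion 6). Section 6.1 lets the investigator stop thalidomide on clinical symptoms, and Section 7.4 allows adjustment for intolerance. No investigator is barred from the stricter action, so the safety risk is softened. These clauses do not say which written dose applies. Since 50 to 100 mg is permitted anyway, some variation in dose between patients is also already part of the design.

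A reader might infer that a patient on 50 mg/d has no defined step in any of the 9 cells under Section 7.4.1. The documents do not support that, because the Appendix 4 ladder implies the next step down. A reader might also infer that Section 7.4.1 becomes the stricter text in every cell once improvement fails. That holds only in the 5 cells named in the working.

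**Conclusion.** The inconsistency is real and worth mending. Section 7.4.1 and Appendix 4 agree on the first action in 0 of 19 triggered cells (0 of 16 on the narrower reading of the trigger), and nothing states which governs, although the cross-reference suggests the table. In 9 cells (8 on the narrower reading) no other grade-based rule clearly settles it; Section 10.2 may reach 4 of them without resolving the conflict.

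The counts take Grade on the Appendix 4 scale, although Section 7.4 names CTCAE 5.0 for adverse events generally. They are counts of table cells, not of patients; the documents do not show how often each cell would occur.

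It would be tempting to infer that the primary result is at risk. The documents do not support that: the complete remission rate hypothesis and the sample size do not depend on this rule. The matter is patient safety and consistent dosing.

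**What to change.** Amend Section 7.4.1 and Appendix 4 together:

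1. Replace the one-level sentence in Section 7.4.1 with a statement that Appendix 4 governs the first action. Keep discontinuation for patients without improvement as the follow-on step.
2. Correct the Grade 2 slight-pain cell so that it is no stricter than Grade 2 with worse pain.
3. State the ladder as 100 mg/d, 50 mg/d, 50 mg every other day, and give the action when a two-level reduction is due in a patient on 50 mg/d.
4. Give the restart dose after a hold.

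Sections 6.2 and 10.2 already send the reader to Section 7.4, so their cross-references can stay. The cost is a wording amendment with written IRB/IEC approval under Section 13.2, plus a clinical decision on items 2 to 4. Sample size, visits and data collection do not change.
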